12.5. Severity Assessment

The investigator will use the adjectives mild, moderate or severe to describe the maximum intensity of each AE. These intensity grades are defined as follows in Table 7.

Table 7: Adverse Effects Assessment

MILD	Does not interfere with subject's usual function
MODERATE	Interferes to some extent (<50%) with subject's usual function
SEVERE	Interferes significantly (≥50%) with subject's usual function

The terms “serious” and “severe” are not synonymous. The term “severe” is often used to describe the intensity (severity) of a specific event. The event itself, however, may be of relatively minor medical significance. This is not the same as “serious,” which is based on

subject/event outcome or action criteria. Accordingly, a severe event is not necessarily a serious event.

12.6. Causality Assessment

The investigator will use the following question when assessing causality of an adverse event to study drug, where an affirmative answer designates the event as a suspected adverse reaction: Is there a reasonable possibility that the drug caused the event? “Reasonable possibility” means that there is evidence to suggest a causal relationship between the drug and the adverse event. The investigator’s assessment of causality must be provided for all AEs. The investigator must record the causal relationship in the CRF, as appropriate, and report such an assessment in accordance with the serious adverse event reporting requirements, if applicable. Regardless of causality, all SAEs are immediately reportable to the Sponsor (see Section 12.9).

12.7. Withdrawal Due to Adverse Events

Withdrawal due to AE should be distinguished from withdrawal due to insufficient response, and recorded on the appropriate AE CRF. When a subject withdraws due to an SAE, the SAE must be reported in accordance with the reporting requirements.

12.8. Eliciting Adverse Event Information and Reporting

The investigator is to report all directly observed AEs and all AEs spontaneously reported by the study subject. Each study subject will be questioned about AEs. Each AE is to be assessed to determine if it meets the criteria for SAEs. If an SAE occurs, expedited reporting will follow appropriate regulations.

12.9. Serious Adverse Event Reporting Requirements

If an SAE occurs, Xeris Pharmaceuticals is to be notified within 24 hrs. of awareness of the event by the investigator, regardless of the investigator’s determination of causality. In particular, if the SAE is fatal or life-threatening, notification to Xeris Pharmaceuticals must be informed as soon as possible, irrespective of the extent of available AE information. This time frame also applies to follow-up on previously forwarded SAE reports.

In the rare event that the investigator does not become aware of the occurrence of an SAE immediately (e.g., an outpatient study subject initially seeks treatment elsewhere), the investigator is to report the event within 24 hrs. after learning such event and document the time of first awareness of the AE.

A death occurring during the study, during the per-protocol follow-up period, or within 4 weeks after stopping treatment with test drug must be reported to Xeris Pharmaceuticals or its designee(s) immediately whether or not it is considered treatment-related. Initial SAE reports must be followed by detailed descriptions. These should include copies of hospital case records and other documents when requested. Telephone reports must be confirmed promptly either by email or overnight courier.

12.10. Non-Serious Adverse Event Reporting Requirements

All AEs will be reported on the AE page(s) of the CRF. AEs should be reported using concise medical terminology on the CRFs as well as on the form for collection of the SAE information.

12.11. Sponsor Reporting Requirements to Regulatory Authorities

AE reporting, including suspected serious unexpected adverse reactions will be carried out in accordance with applicable regulations.

The investigator also must notify the IRB of the occurrence of all SAEs, in writing, as soon as is practicable and in accordance with local regulations. A copy of this notification must be provided to Xeris Pharmaceuticals or its designee.

In the event of an SAE that meets the criteria for expedited reporting, an SAE report will be prepared for submission to the FDA and any other applicable authorities by Xeris Pharmaceuticals or its designee.

12.12. Pregnancy

This is not applicable since all subjects are under 1 year of age.

12.13. Subject Monitoring

Subjects will be monitored for AEs throughout the study by the study unit staff. The principal investigator or designated sub-investigator will be on site for initial pump placement and for the subsequent 4 hours. The principal investigator or designated sub-investigator will also be on call for the remainder of the study. As necessary, a physician will administer treatment for any AEs.

Safety parameters, including laboratory results, will be assessed by the principal investigator or his delegate using the site's criteria for clinical laboratory acceptance ranges as suggested guidelines in making the medical assessment.

Scheduled safety measurements will be repeated according to appropriate SOPs or upon request from a physician. Any abnormal repeated measurement will be evaluated by a physician and repeated if judged necessary. Further action may be taken on the physician's request.

12.14. Medical Device Reports

A reportable medical device report (MDR) is one for which there is a reasonable possibility that a device has or may have caused or contributed to a death or serious injury.

Caused or contributed means that a death or serious injury was or may have been attributed to a medical device, or that a medical device was or may have been a factor in a death or serious injury, including events occurring as a result of:

- (1) Failure;
- (2) Malfunction;
- (3) Improper or inadequate design;
- (4) Manufacture;

- (5) Labeling; or
- (6) User error.

Serious injury means an injury or illness that:

- (1) Is life-threatening,
- (2) Results in permanent impairment of a body function or permanent damage to a body structure, or
- (3) Necessitates medical or surgical intervention to preclude permanent impairment of a body function or permanent damage to a body structure.

All reportable MDRs will be reported to Xeris within 24 hours of an investigator's first awareness of the event. For all reportable MDRs, within 10 working days of becoming aware of the event, the investigator will complete Med Watch Form FDA 3500A for submission to FDA, in the case of a device-related death, or to the device manufacturer, in the case of a device-related serious injury.

13. DATA ANALYSIS AND STATISTICAL METHODS

13.1. Sample Size Determination

This is a parallel group adaptive design with one interim analysis after 6 subjects in each study arm have completed their post-treatment success-failure determination. Depending on the comparison of the treatment and placebo failure rates, the study will either be stopped with an early claim for treatment efficacy, or continued with either 3 or 6 additional subjects per study arm so that the final comparison of failure rates will be based on 9 or 12 subjects per study arm. The final sample size will be based on the outcome of the interim analysis.

The criteria for stopping early at 6 subjects per group or continuing to a final sample size of 9 or 12 subjects per group was designed so that the type 1 error is no larger than 0.025 for treatment = control failure rates at any failure rate. The overall power for concluding that the treatment failure rate is less than control is over 98% if the placebo failure rate is at least 0.9 and the treatment rate is no more than 0.1, with early efficacy having a power of 66%. If the placebo failure rate is at least 0.95 and the treatment failure rate is no more than 0.05 then the chance for an early efficacy determination is 88%.

Power and type 1 error levels were computed using Monte Carlo simulations of the study, 10,000 replications for each determination (R, version 3.1.2).

13.2. Statistical Analyses

The pharmacodynamic endpoints will be derived from the individual glucose infusion rates (GIRs).

Primary and secondary efficacy analyses will be performed using two cohorts of subjects:

- Primary cohort defined as all subjects fulfilling final protocol GIR selection criteria having average GIR assessments at periods 1, 2.
- Per-Protocol cohort defined as subjects from the Primary cohort having no major protocol violations.

The primary endpoint will be based on the Primary cohort. The safety analyses will use the Safety cohort defined as all subjects receiving either of the treatment regimens.

13.2.1. Primary Endpoint (Pharmacodynamic)

For each subject, the average GIR will be computed for periods 1 (baseline), 2 (treatment) by determining the area under the curve of GIR excluding the first 2 hours versus time and then dividing by the time duration for each of the periods excluding the first 2 hours using the last 24 hours for each period, or if less than 24 hours is available, the available data excluding the first 2 hours.

The primary comparison of treatment and placebo will be based on a success-failure determination (see Section 5.1).

This is a parallel group, adaptive design with one interim analysis after 6 subjects in each study arm have completed their success-failure determination. If, at the interim analysis, the observed

treatment failure rate is lower than placebo so that the one-tailed p value is less than or equal to 0.0124 (Fisher's exact test, hypergeometric distribution based on the total number of failures) then the study will be stopped due to early treatment efficacy.

If this interim one-tailed p value is greater than 0.0124 but less than or equal to 0.05, then the study will continue and an additional 3 more subjects per study arm will be randomized. If this interim one-tailed p value exceeds 0.05 then the study will continue, and an additional 6 more subjects will be randomized. The final analysis will be based on the observed treatment and placebo failure rates using all subjects with a success-failure determination. If, at the final analysis, the observed treatment failure rate is lower than placebo so that the one-tailed p value is less than or equal to 0.04 (hypergeometric distribution) then treatment efficacy will be established.

The actual type 1 errors are smaller than the efficacy criteria would suggest because of the small sample sizes and the use of Fisher's exact test. From Monte-Carlo simulations the overall type 1 error for this design is bounded above by 0.016 for null hypothesis treatment = placebo failure rates at any failure rate using the above criteria. The type 1 error achieves its maximum at treatment = placebo = 0.5, and for this design the maximum is 0.016 as estimated by 10,000 Monte Carlo replications of the design.

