If this interim hypergeometric one-tailed p value is greater than 0.0124 but less than or equal to 0.05, then the study will continue and an additional 3 more subjects per study arm will be randomized. If this interim one-tailed p value exceeds 0.05 then the study will continue, and an additional 6 subjects will be randomized. The final analysis will be based on the observed treatment and placebo failure rates using all subjects with a success-failure determination. If, at the final analysis, the observed treatment failure rate is lower than placebo so that the one-tailed hypergeometric p value is less than or equal to 0.04 then treatment efficacy will be established

The actual type 1 errors are smaller than the efficacy criteria would suggest because of the small sample sizes and the use of Fisher's exact test. From Monte-Carlo simulations the overall type 1 error for this design is bounded above by 0.016 for null hypothesis treatment = placebo failure rates at any failure rate using the above criteria.

Secondary analyses will include baseline adjusted analyses of the natural logarithm of GIR to obtain confidence bounds on ratio of treatment to placebo mean GIR. Other secondary endpoints will consider the average GIR over the last 24 hours during period 2. The chance that this final rate is less than 8 mg/kg/min will be estimated and compared. Also, the cumulative glucose infusion will be combined with the total enteric feeding for the last 24 hours. The chance that this combined value is less than or equal to 8 mg/kg/min will be estimated and compared.

Pharmacokinetic (PK) data of steady state glucagon concentrations following continuous subcutaneous infusion will be analyzed descriptively.

Safety analysis: all subjects who have received at least one dose of study medication will be included. Safety data will be presented in tabular and/or graphical format and summarized descriptively. For continuous data, change from baseline will be analyzed using analysis of covariance. The proportion of study participants experiencing a particular AE will be compared by group (dose) using Fisher's Exact Test.

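### The type 1 error stated as bounded by 0.016 is in fact 0.0169 at its exact maximum; a minor correction, since the 0.025 limit is still met

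*Combined protocol and SAP*

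**What the plan says.** Section 13.2.1 sets out a two-stage comparison of failure rates, with "one interim analysis after 6 subjects in each study arm have completed their success-failure determination". The trial stops for efficacy if "the one-tailed p value is less than or equal to 0.0124 (Fisher's exact test, hypergeometric distribution based on the total number of failures"). If the interim p value lies above 0.0124 but not above 0.05, "an additional 3 more subjects per study arm will be randomized". For larger p values the rule reads: "If this interim one-tailed p value exceeds 0.05 then the study will continue, and an additional 6 more subjects will be randomized". That sentence does not say per arm, but Sections 13.1 and 13.4 do, and Section 13.1 gives final sizes of 9 or 12 per arm. At the end, if the "one-tailed p value is less than or equal to 0.04 (hypergeometric distribution) then treatment efficacy will be established".

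Three statements concern the error rate:

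- Section 13.1 gives the design limit: "the type 1 error is no larger than 0.025 for treatment = control failure rates at any failure rate".
- The Synopsis (Bio-statistical Considerations) and Section 13.2.1 both report, from simulation, that "the overall type 1 error for this design is bounded above by 0.016" whatever the common failure rate.
- Section 13.2.1 adds that the maximum occurs at 0.5 and that "for this design the maximum is 0.016 as estimated by 10,000 Monte Carlo replications of the design".

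**The concern.** A bound on type 1 error is a claim about the worst case, and a simulated proportion is an estimate with error on both sides. Quoting a 10,000-run estimate as a bound is unsafe whenever the true value could lie above it. Here simulation is also unnecessary, because every outcome of a design with at most 12 per arm can be listed and weighted exactly.

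At stake is the accuracy of a stated operating characteristic of the primary test. If the true maximum were close to or above 0.025, the primary claim itself would be in question, so the size of the discrepancy has to be established.

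**Working it through.** **Inputs** (Sections 13.1 and 13.2.1): 6 per arm at the interim; stop if the one-tailed Fisher p ≤ 0.0124; add 3 per arm if 0.0124 < p ≤ 0.05; otherwise add 6 per arm; final one-tailed Fisher p ≤ 0.04 on all data; limit 0.025; 10,000 replications.

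**Method.** For a treatment failure rate a and a placebo failure rate b, each interim table (t, c) has probability Bin(t; 6, a) × Bin(c; 6, b). Tables that stop count as rejections. The others are extended by all possible second-stage results, and those with a final p ≤ 0.04 are added. Type 1 error sets a = b = p and is maximised over p.

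**Interim tables with p ≤ 0.05** (treatment v placebo failures):

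| Table | p | Action |
|---|---|---|
| 0 v 6 | 0.0011 | stop |
| 0 v 5, 1 v 6 | 0.0076 | stop |
| 0 v 4, 2 v 6 | 0.0303 | go to 9 per arm |
| 1 v 5 | 0.0400 | go to 9 per arm |

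**Step 1: reproduce the plan's power.**

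- Early stop at 0.9 v 0.1: 0.9^6 = 0.5314 and 6 × 0.1 × 0.9^5 = 0.3543. Then 0.5314² + 2 × 0.5314 × 0.3543 = 0.659 (stated 66%).
- Early stop at 0.95 v 0.05: 0.7351² + 2 × 0.7351 × 0.2321 = 0.882 (stated 88%).
- Overall power at 0.9 v 0.1, by full enumeration: 0.990 (stated over 98%).

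The design has therefore been read as its authors meant it.

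**Step 2: type 1 error at p = 0.5.**

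- Interim stop: (1 + 6 + 6)/4096 = 0.00317
- Rejection at 9 per arm: 0.00554
- Rejection at 12 per arm: 0.00811
- Total: 0.01682

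**Step 3: other common failure rates.** The null curve is symmetric about 0.5.

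| p | Type 1 error |
|---|---|
| 0.30 or 0.70 | 0.01561 |
| 0.35 | 0.01663 |
| 0.40 or 0.60 | 0.01685 |
| 0.45 | 0.01684 |
| 0.50 | 0.01682 |

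The maximum is 0.01686, just inside 0.60 and, by symmetry, 0.40. The stated 0.016 is exceeded at 0.5 itself, and already at 0.35.

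**Step 4: could simulation have given 0.016?** The standard error is √(0.0169 × 0.9831/10,000) = 0.0013. Then (0.0169 − 0.016)/0.0013 ≈ 0.7 standard errors, so yes. Ten repeat simulations at 0.5 ranged from 0.0157 to 0.0188. An observed 0.016 is compatible with true values up to about 0.016 + 1.96 × 0.0013 = 0.0185.

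**Step 5: does another reading rescue the figure?** If the second extension meant 6 in total (3 per arm), the maximum would be 0.01648. That rounds to 0.016 but still exceeds it. Overall power would fall to 97.2%, against the stated figure of over 98% and the stated 12 per arm.

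**Step 6: margin to the limit.** 0.025 − 0.0169 = 0.0081, about a third of 0.025.

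**The case against.** The strongest defence is that nothing depends on the discrepancy. The text says openly that the figure comes from simulation, the gap is less than one standard error of that simulation, the curve is flat around its peak, and the limit that matters is 0.025. All of this stands, and it is why the point is minor. It does not rescue the word bound, or the claim that 0.016 holds at any failure rate.

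A reader might go further in two ways that the documents do not support.

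- *That the design fails to control type 1 error.* It does not fail: 0.0169 is below 0.025 at the planned sizes. Placing the peak at 0.5 rather than near 0.4 and 0.6 changes the fifth decimal (0.01682 v 0.01686).
- *That the unspent third of 0.025 is waste, and the final cutoff should rise to 0.045.* At exactly 6, 9 or 12 per arm, 0.045 would keep the maximum at 0.0229 and raise power at, say, 0.8 v 0.3 from 62.9% to 67.4%. But the Synopsis and Section 13.2.1 say that the actual error is smaller than the cutoffs suggest, and nowhere does the plan aim to use all of 0.025. At the plan's own rates of 0.9 v 0.1 the gain is 99.0% to 99.2%. Nor are the planned counts guaranteed. Section 9.1 triggers the interim at 12 evaluable patients in total, allocates by minimization on baseline GIR and replaces non-evaluable patients, while Section 13.2.1 analyses everyone with a success-failure determination.

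The documents give no overrun figures, so the following splits are assumptions. Each adds 3 per arm in the first extension.

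| Interim, then second-extension final | Max at 0.04 | Max at 0.045 |
|---|---|---|
| 6:6, then 14:13 | 0.0219 | 0.0288 |
| 7:5, then 14:11 | 0.0216 | 0.0288 |
| 7:6, then 14:13 | 0.0212 | 0.0274 |
| 6:6, then 13:12 | 0.0244 | 0.0245 |

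The first three break the limit at 0.045 but not at 0.04. The last shows that a single extra subject can use up most of the margin at 0.04. The protection is not complete: of 176 small departures tried, 34 exceeded 0.025 at 0.045 and 5 did so at 0.04.

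**Conclusion.** The stated bound is wrong by a small amount. The exact maximum type 1 error is 0.0169, against 0.016, an excess of 0.0009. The stated powers reproduce, so the fault lies in treating a simulated estimate as a bound and not in the design. The 0.025 limit is met, and the cutoffs, sample sizes and conclusions are unaffected. This is a minor correction of a stated figure.

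The result assumes exactly 6, then 9 or 12, evaluable subjects per arm, independent binomial outcomes, and the second extension read as 6 per arm, as Sections 13.1 and 13.4 have it.

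**What to change.** In the Synopsis (Bio-statistical Considerations) and Section 13.2.1, replace the simulated bound with the exact result. The text should say that, by enumeration, the maximum one-sided type 1 error is 0.017 for the planned 6, 9 or 12 evaluable subjects per arm, reached at common failure rates of about 0.4 to 0.6, and that this is below the 0.025 limit. In Section 13.2.1, drop the sentence that puts the maximum at 0.5 and cites 10,000 replications for it.

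Leave the final cutoff at 0.04. The cost is a few lines of text and a short enumeration to keep on file. The decision rule does not change.

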13.2.2. Secondary Endpoints (Pharmacodynamic)

Secondary analyses will include baseline adjusted analyses of the natural logarithm of GIR to obtain confidence bounds on ratio of treatment to placebo mean GIR.

Other important secondary endpoints will consider the average GIR over the last 24 hours during period 2. The chance that this final rate is less than 8 mg/kg/min will be estimated and compared. Also, the cumulative glucose infusion will be combined with the total enteric feeding for the last 24 hours. The chance that this combined value is less than or equal to the daily equivalent of 8 mg/kg/min will be estimated and compared.

Furthermore, the following secondary endpoints will be described:

- Discontinuation of feeds with ability to fast for 3 hours
- Discontinuation of Gastrostomy tube (G tube) of glucose infusion

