5.2. Secondary Objectives

The secondary objectives are to:

1. Compare average proportional GIR reduction from baseline between CSI-Glucagon™ and placebo.
2. Compare the percentage of subjects in each group that achieve $\text{GIR} \leq 8$ mg/(kg*min) during treatment.
3. Compare the percentage of subjects in each group that achieve daily total caloric intake from carbohydrate, combining oral, tube and IV sources \leq equivalent to 8 mg/(kg*min) glucose.
4. Describe the proportion of subjects in each group that discontinue IV glucose infusion as well as the proportion of subjects that discontinue continuous naso-gastric feeds (ability of patient to fast for 3 hrs.).
5. Compare proportional time < 70 mg/dL as well as proportional time in euglycemia (≥ 70 mg/dL and < 180 mg/dL) from CGM assessments.
6. Compare device performance between the groups, including:
 - weight-based estimate of dose volume delivery
 - infusion site leakage
 - device failures/malfunctions
7. Assess safety of pump switch out procedure as assessed by occurrence of glucose < 50 mg/dL by continuous glucose monitoring.
8. Evaluate the safety and tolerability of CSI-Glucagon™ administered from an OmniPod® pump by assessing the following endpoints:
 - Incidence of adverse events (AEs) and serious adverse events (SAEs)
 - Laboratory safety variables
 - Physical examination
 - Vital signs

- Local tolerability: Erythema and/or edema formation at site of infusion assessed using the Draize scale

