10.2.2. Period 2: Blinded, Randomized Treatment (Days 0-1)

Once baseline GIR has been established in Period 1, the following procedures will be completed, including initiation of blinded study treatment.

Day 0

1. If not inserted during Period 1, insert CGM (Dexcom® G4 Platinum) and calibrate per manufacturer. Stabilize for a minimum of 2 hours and confirm CGM is reporting glucose values before proceeding to step 2.
{Note: The CGM will be used for rapid alerts, which will trigger POC assessments of blood glucose that will be used to guide clinical decisions.}
2. Draw blood for plasma insulin and glucagon levels and immunogenicity testing (as listed in [Table 5](#)), prior to application of the OmniPod® pump.
3. Photograph the site of approximate cannula insertion prior to application of the OmniPod® pump.
4. Using the appropriate syringe (see [Section 9.3.3](#)), load a fresh OmniPod® pump with 1 mL CSI-Glucagon™ solution (5 mg/mL concentration) or placebo as per the randomization scheme.
5. Study staff will weigh the loaded pump to the nearest whole mg (see [Appendix 2](#)), and then apply the OmniPod® pump to the abdomen of the subject (see [Section 9.1](#)).
6. Use the PDM to instruct the pump to insert the cannula and ensure deployment as follows:

- Listen for an audible “click.”
 - Confirm pink slide insert has moved into the window on the surface of the pump, indicating deployment.
 - Use the clear window on one end of the pump to view the inserted cannula.
7. Once cannula deployment is confirmed, set basal rate at 5 µg/kg/hr. Record time of starting the pump; this is t=0.
 8. Monitor POC glucose every hour for the first three hours after study drug start and every 3 hours thereafter; or more frequently if the CGM shows glucose falling <70 mg/dL (3.9 mmol/L) or rising above >200 mg/dL (11.1 mmol/L). Additionally, the trajectory of change in plasma glucose concentration based on the two most recent POC measurements should be used to adjust the frequency of glucose monitoring as needed to prevent plasma glucose <70 mg/dL (3.9 mmol/L) or >200 mg/dL (11.1 mmol/L).
 9. Adjust IV fluids as per period 1 with the following additions:
 - a. If POC glucose is >70 mg/dL (3.9 mmol/L) and GIR=0, introduce and/or extend the fasting period after meal feeding as long as possible, while maintaining POC glucose > 70 mg/dL.

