If GIR=0, continuous enteric feeding has been completely weaned, and plasma glucose continues to rise, reduce study drug infusion rate by 2.5 $\mu\text{g}/\text{kg}/\text{hr}$ every 6 hours to a minimum of 2.5 $\mu\text{g}/\text{kg}/\text{hr}$, as long as the pre-meal blood glucose is >70 mg/dL (3.9 mmol/L).

At approximately 48 hours from the start of the first blinded study treatment, complete the following:
 - b. Draw blood for insulin and glucagon levels as well as CBC and CMP.
 - c. Remove the OmniPod® pump, weigh it, and photograph the application site, paying particular attention to the cannula insertion site.
 - d. Assess site for edema and erythema using the Draize scale. Any Draize scores > 0 should be followed to resolution, including a follow-up photograph.
 - e. Proceed to Period 3 (see 10.2.3).

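### The log-GIR secondary analysis has no rule for a zero average, and the average it would use by default covers hours 2-24 for infants who fail at 24 h but hours 24-48 for those who complete 48 h

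*Combined protocol and SAP*

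**What the plan says.** Section 5.2 gives secondary objective 1 as "Compare average proportional GIR reduction from baseline between" the two arms. The only analysis of GIR reduction in Section 13.2.2 is "baseline adjusted analyses of the natural logarithm of GIR to obtain confidence bounds on ratio of treatment to placebo mean GIR"; the Synopsis repeats it. Neither place says which average is logged or what happens to a zero.

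Section 13.2.1 defines an area-under-the-curve average for Periods 1 and 2, "using the last 24 hours for each period, or if less than 24 hours is available, the available data excluding the first 2 hours". The GIR <8 mg/kg/min endpoint in 13.2.2 "will consider the average GIR over the last 24 hours during period 2", and for the carbohydrate endpoint "the cumulative glucose infusion will be combined with the total enteric feeding for the last 24 hours".

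A GIR of zero is foreseen. Section 10.2.2 tells staff that, when POC glucose is above 70 mg/dL "and GIR=0, introduce and/or extend the fasting period after meal feeding as long as possible", and the Day 1 text covers the case "If GIR=0, continuous enteric feeding has been completely weaned, and plasma glucose continues to rise". Section 5.2 also sets out to "Describe the proportion of subjects in each group that discontinue IV glucose infusion".

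Under Sections 7.1, 10.2.2 and 10.2.3, an infant whose average GIR has fallen by less than 20% at 24 h moves to open-label drug then. The others stay on blinded treatment to 48 h.

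**The concern.** There are two separate problems.

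**Zeros.** An infant with no IV glucose throughout hours 24-48 has a possible best outcome on this endpoint, yet the planned analysis cannot use the value. Whoever runs the analysis must drop the infant, add a constant or set a floor. In arms of 6 to 12 that choice largely fixes the estimate and its interval. If it is made after unblinding, it cannot be defended as neutral.

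**Windows.** Period 2 ends at 24 h for an early failure and at 48 h otherwise, so the 13.2.1 rule averages the two kinds of infant over hours that do not overlap. Most placebo infants are expected to fail and most treated infants to succeed, so the arms would be compared largely on different days. The GIR <8 and carbohydrate endpoints share this feature.

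**Working it through.** **The plan's own figures.** The documents give no figure for the log-GIR analysis. The relevant stated figures are the chances of stopping at 6 per arm (Section 13.1: 66% and 88%), since the zero problem is worst there. One-tailed Fisher p ≤ 0.0124 needs placebo-treated failures of 6-0, 6-1 or 5-0 (p = 0.0011, 0.0076, 0.0076).
- Failure rates 0.9 v 0.1: P(6 of 6 placebo fail) = P(0 of 6 treated fail) = 0.9^6 = 0.531. P(5 of 6 placebo fail) = P(1 of 6 treated fails) = 6 × 0.1 × 0.9^5 = 0.354. Total 0.531² + 2 × 0.531 × 0.354 = 0.659.
- Rates 0.95 v 0.05: 0.735² + 2 × 0.735 × 0.232 = 0.882.

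Both reproduce.

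**Can the average be zero?** Using the weaning steps in Section 10.2.1, a GIR of 8 mg/kg/min reduced by 1 every 3 h takes eight steps and reaches 0 by about hour 24. A GIR of 12 reduced by 2 every hour takes six steps, about 6 h. So a zero average over hours 24-48 is reachable. Only infants who continue past 24 h can have one, and GIR must stay at 0 for the whole window. The documents do not say how often this would happen.

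**Effect of one zero.** All inputs here are assumptions: median baseline 12 mg/kg/min (log SD 0.3), on-treatment median 12 on placebo and 6 on active (true ratio 0.50), log SD 0.2 about those, and one treated infant of n at zero. If a constant c is added before logging, the ratio is approximately

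(6 + c)/(12 + c) × [c/(6 + c)]^(1/n).

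For c = 0.1 and n = 6: 0.504 × (0.1/6.1)^(1/6) = 0.504 × 0.504 = 0.25. Simulated trials (4,000 per size, ANCOVA of log GIR on log baseline) give these median estimates and 95% limits:

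| Rule for the zero | 12 per arm | 6 per arm |
|---|---|---|
| add 1 | 0.46 (0.31-0.67) | 0.39 (0.17-0.88) |
| add 0.1 | 0.36 (0.17-0.76) | 0.25 (0.05-1.33) |
| add 0.01 | 0.29 (0.09-0.93) | 0.17 (0.01-2.21) |
| drop the infant | 0.50 (0.42-0.60) | 0.50 (0.38-0.67) |

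**Near-zero values need no rule but act the same way.** Three hours at 1 mg/kg/min within 24 h averages 3/24 = 0.125. At 6 per arm the ratio is 0.5 × (0.125/6)^(1/6) = 0.26, with simulated interval 0.05-1.25. At log SD 0.2 that interval includes 1 in about 81% of trials, against under 1% without the low value. At log SD 0.4 the contrast is about 77% against 28%. At 12 per arm and log SD 0.2 the ratio is 0.36 (0.18-0.74), and the interval includes 1 in about 1% of trials.

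**Effect of the windows.** Assumptions: day-1 GIR as a fraction of baseline has median 0.55 on active and 1.0 or 0.85 on placebo, log SD 0.2. Failure at 24 h means a fraction above 0.80.
- Share failing at 24 h: placebo Φ(ln(1.0/0.80)/0.2) = 87% or Φ(ln(0.85/0.80)/0.2) = 62%; active 3%.
- Shared change, day 2 = day 1 × r: the mixed ratio equals the day-1 ratio times r^(placebo share − active share). With 87% failing, 0.8^0.84 = 0.83 and 1.2^0.84 = 1.17. With 62% failing, 0.8^0.59 = 0.88 and 1.2^0.59 = 1.11.
- No shared change, day-1 variation all within-infant noise: early failures keep their high day-1 value while the others are re-measured. Each arm's mean log shifts by 0.2 × φ(k), where φ is the standard normal density and k = ln(0.80/median)/0.2. The shifts are 0.014 (active), 0.043 (placebo 1.0) and 0.076 (placebo 0.85). Multipliers: exp(0.014 − 0.043) = 0.97 and exp(0.014 − 0.076) = 0.94.
- No shared change and day-1 variation all persistent: multiplier 1.00.

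Changing the scale does not cure this. At r = 0.8 with 87% failing, the arm difference in proportional reduction is 46 points on day 1, 37 on day 2 and 55 in the mixed window.

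**The case against.** - **The average is not really undefined.** Section 13.2 sets the cohort for primary and secondary efficacy analyses by the availability of average GIR in Periods 1 and 2, and 13.2.1 then defines that average. The averages in 10.2.1 and 10.2.2 serve bedside decisions. This stands: a reader might infer that the plan leaves the logged quantity open, but 13.2.1 is the clear default. What remains is that 13.2.2 does not say so, and that 10.2.1 calls a different quantity the baseline.
- **A passing GIR of zero does not break the logarithm.** Correct. The average must be zero over the whole window, and the frequency is unknown. Stopping IV glucose is also described separately. This limits how likely the problem is, but does not supply the missing rule.
- **The window rule is stated, and no blinded day-2 value can exist for early failures.** Also correct. The last blinded 24 h is a coherent summary of treatment while blinded. It is not an estimate of the effect on either day, and nothing in the plan labels it as mixing days.
- **The simulated contrast depends on the assumed SD.** It does: 81% against under 1% becomes about 77% against 28% when the log SD is doubled. The shift in the ratio itself is stable.
- **Only secondary analyses are involved.** This stands and sets the severity.

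A reader might also infer that the window rule favours the drug, or that it matters only if GIR falls over time in both arms. Neither follows. A shared rise pushes the ratio against treatment, noise alone shifts it with no drift, and a day-2 fall caused by the drug is effect rather than bias. The documents establish no drift in either direction. Nor is there type 1 error inflation: if the arms behave identically, the same rule applies equally to both and the ratio is 1.00.

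**Conclusion.** The point holds, as a minor to moderate issue for secondary analyses. As written, the log ratio cannot be computed if any infant's average is zero, and one near-zero average can dominate it. With one zero and a true ratio of 0.50, the estimate ranges over 0.29-0.50 at 12 per arm and 0.17-0.50 at 6 per arm, according to a rule the plan does not give. Separately, the default average lets the 24-h outcome choose the hours compared. The illustrated multipliers on the day-1 ratio are 0.83 to 1.17 for shared factors of 0.8 to 1.2 with 87% of placebo failing at 24 h, and 0.97 or 0.94 from noise alone.

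The GIR levels, SDs, number of zeros and day-to-day factors are all assumptions. The documents support the possibility of zeros and the existence of two windows, not their frequency or the direction of any bias. A reader might infer that the trial's main conclusion is at risk; it is not, because the Fisher test and the interim rules use success or failure only.

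**What to change.** Before the unblinded interim, amend Section 13.2.2 and the matching Synopsis text.

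- **Main scale.** Analyse secondary objective 1 as untransformed proportional change in average GIR, by ANCOVA on baseline GIR. A zero then counts as a 100% reduction. Under the same assumptions, one zero moves the arm difference from about 51 to 55 points at 12 per arm and to 59 at 6 per arm. State one baseline definition, reconciling 10.2.1 (average during weaning) with 13.2.1 (last 24 h of Period 1).
- **Windows.** Report this and the GIR <8 endpoint over hours 2-24 for every infant with 24 h of blinded data, beside the last-24-h version labelled as mixing windows. State in advance which is the main result. Do the same for total carbohydrate only if oral and tube intake over those hours is recorded.
- **Log ratio.** If it is kept as supportive, state which average is logged and the rule for zeros.

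Cost: a protocol amendment with IRB approval (Section 18.1). GIR needs no new data, because Section 10.2.2 already requires the hours 2-24 average at 24 h. The downside is that hours 2-24 include up-titration and omit day 2 of a two-day objective, so the effect may look smaller. That is why both windows should be shown.
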